### 9.8.3. Laboratory Data

All laboratory data will be converted to standard units and classified into CTC grades according to the NCI CTCAE v4.03.

Shift tables using CTC grades to compare baseline value to the worst post-baseline value will be produced for hematology and biochemistry laboratory parameters with CTC grades. Scheduled as well as unscheduled assessments will be considered.

The serum chemistry and hematology data will also be displayed graphically for phase II – for each parameter, mean  $\pm$  SE will be plotted by visit.

The listings for serum chemistry, hematology and urinalysis data will include all results, investigator’s assessment of clinical significance and abnormal values will be flagged.

### 9.8.4. Vital Signs

Values for vital signs and change from baseline for relevant parameters (systolic and diastolic blood pressure, pulse rate, weight) will be summarized by pre-specified categories as per the criteria specified in [Table 1](#) . The listings will include results and investigator’s assessment of clinical significance.

*Table 1 Criteria of Potential Clinical Concern for Vital Signs*

Parameter	Lower limit	Upper limit
Systolic BP (mm Hg)	min. $\leq 90$	max. $\geq 160$
Systolic BP (mm Hg) change from baseline	max. decrease $\geq 20$	max. increase $\geq 20$
Diastolic BP (mm Hg)	min. $\leq 50$	max. $\geq 100$
Diastolic BP (mm Hg) change from baseline	max. decrease $\geq 10$	max. increase $\geq 10$
Pulse rate (bpm)	min. $< 50$	max. $> 100$
Pulse rate (bpm) change from baseline	max. decrease $\geq 15$	max. increase $\geq 15$

### 9.8.5. Other Safety Data

Values for ECG parameters QT (variable name “QTSB”) and QTcF (variable name “QTcFSB”) will be averaged over the three measurements coming from each triplicate assessment and summarized by descriptive statistics for continuous data. In addition, the number and percentage of patients having values

- >30ms and >60ms for the change from baseline
- >450ms, >480ms, and >500ms for the absolute values

will be presented.

For Cycle 1 Day 1 all post-dose time-points and Cycle 1 Day 15 the pre-dose and all post-dose time-points, the relationship between ECG parameters and AK-01 exposure will be explored by plotting

- Absolute QT and QTcF values versus plasma concentrations
- Change from baseline in QT and QTcF values versus plasma concentrations

All ECG data will be listed. The ECOG evaluations will be listed.

## 9.9. Pharmacokinetic Analyses

All PK analyses (except dose proportionality assessment) will be performed by CiTox Lab (Quebec, Canada).

The PK analyses will be performed on the PK analysis set.

### 9.9.1. Values Below the Limit of Quantitation or Missing

For the calculation of PK parameters, all plasma concentrations that are below the limit of quantitation (BLQ) before the first measurable concentration will be set to zero. The BLQ values that are between measurable concentrations and that occur after the last quantifiable concentration will be set to missing. Concentrations that are BLQ will be treated as zero for descriptive statistics. All missing concentrations will be treated as missing for descriptive statistics and calculation of PK parameters.

### 9.9.2. Blood Sample Collection

As per the PK sampling schedule, the following measurements will be available

- For Day 1 and 15 (Cycle 1): PK concentrations at 0 hours (pre-dose) and 1, 2, 4, 6, and 8-12 hours post-dose
- For Day 2 and 8 (Cycle 1): PK trough (pre-dose) concentrations

### 9.9.3. Graphical Analyses

Mean plasma concentration data of AK-01 versus nominal time will be plotted by day and the actual dose administered before the sampling for Phase I and by tumor type, day and dose for Phase II, separately, on linear and semi-logarithmic scales. Mean plots will include all doses and both sampling days. Samples that are +/- 10% outside of the scheduled sampling time will be excluded from this analysis. Individual plasma concentration data of AK-01 versus actual times

will also be presented on linear and semi-logarithmic scales for Phase I and Phase II, separately. Both days will be shown superimposed on each individual plot. Additionally, overlay plots of individual plasma concentration data of AK-01 versus actual times will be presented by study day and dose, on linear and semi-logarithmic scales for Phase I and Phase II, separately. A mean dose-normalized plot of average concentrations versus time will be generated for Phase I; for both days.

#### 9.9.4. PK parameters

PK parameters for Day 1 and 15 will be calculated individually by standard non-compartmental methods of analysis by CiTox Lab, using Phoenix® WinNonlin® Version 6.2 or higher (Pharsight, St. Louis, MO, USA). The individual concentration versus actual time data for plasma AK-01 will be used to derive the following PK parameters:

AUC0-t	Area under the plasma concentration versus time curve from time 0 to the last quantifiable concentration, using the linear trapezoidal rule
AUC0-12	Area under the plasma concentration versus time curve from time 0 to 12 hours post-dose, using the linear trapezoidal rule
AUC0-24	Area under the plasma concentration versus time curve from time 0 to 24 hours post-dose, based on AUC0-12 data
AUC0-∞	Area under the plasma concentration versus time curve from time 0 to infinity using the linear trapezoidal rule, calculated as $AUC0-t + C_{last}/k_{el}$ , where $C_{last}$ is the last measurable concentration
Cavg	Average plasma concentration throughout a sampling day
Cmax	Maximum plasma concentration
tmax	Time to reach maximum plasma concentration
kel	Elimination rate constant, estimated by linear regression of the terminal portion of the log-concentration by time curve; a minimum of 3 non-BLQ data points in the elimination phase (not including Cmax) will be used for the calculation. The kel may not be estimated if r-squared is less than 0.8.
t1/2	Apparent terminal elimination half-life, calculated as $(\ln 2)/k_{el}$
CL/F	Apparent clearance, calculated as $Dose/AUC0-24$ (Day 15 only)
Vz/F	Apparent volume of distribution, calculated as $Dose/(AUC0-24 * k_{el})$ (Day 15 only)
LI	Linearity index, calculated as: $AUC0-24 [Day 15] / AUC0-∞ [Day 1]$
Rac(AUC)	Accumulation ratio (based on AUC), calculated as $AUC0-12$ after last dose on Day 15 / $AUC0-12$ after a single dose [Day 1]

Rac(Cmax) Accumulation ratio (based on Cmax), calculated as Cmax after last dose on Day 15 / Cmax after a single dose [Day 1]

Plasma PK parameters for AK-01 will be summarized by AK-01 dose level and day using descriptive statistics (number of non-missing observations, mean, standard deviation, CV%, median, minimum, and maximum) for Phase I and by tumor type for Phase II, separately. In addition, geometric mean, standard deviation of log-transformed data and geometric CV% will be calculated for all parameters except tmax.

Values for AUC0-∞, kel, LI, Vz/F, or t1/2 will not be reported for cases that do not exhibit a terminal log-linear phase of the concentration-time curve.

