**Table 1. AK-01 Dose Modifications for Toxicity**

Toxicity	Dose Modification
QTcF Prolongation	
<Grade 2	Continue at current dose level.
Grade 2 (QTcF average of triplicate readings >480 msec)	Reduce dosing frequency without interruption. If the event recurs, the dose may be withheld. If the event recurs a third time, dosing may only continue with sponsor approval.

Grade 3 (QTcF average of triplicate readings >500 msec)	Withhold AK-01 for up to 14 days. If QTcF returns to within 30 msec of baseline or <450 msec within 14 days, treatment may be resumed at a reduced dosing frequency. If the event recurs a second time, the dose may again be withheld and resumed after 14 days providing the above criteria are met after 14 days. If a third occurrence is documented, treatment must be terminated.
Grade 4 (QTcF average of triplicate readings >500 msec or >60 msec change from baseline, and TdP or polymorphic ventricular tachycardia or signs/symptoms of serious arrhythmia)	Treatment should be terminated.
Other Non-Hematologic Toxicity	
Grade ≤2	Continue at current dose level.
Grade 3 (except alopecia, nausea, vomiting or diarrhea) not optimally managed per institutional guidelines	Withhold AK-01 until event returns to Grade 1 or baseline. The first time the event occurs, maintain the AK-01 dose level when dosing is resumed.  Each time the Grade 3 event recurs, withhold AK-01 until event returns to Grade 1 or baseline, then decrease AK-01 dosing frequency- when dosing is resumed. If the event recurs at 25 mg QD, the patient will be withdrawn.
Grade 4 (except alopecia, nausea, vomiting or diarrhea) not optimally managed per institutional guidelines	Patient will be withdrawn. Patient may not be rechallenged unless discussed with sponsor and approved by the SAC.
Hematologic Toxicity	
Platelets ≤Grade 1  ANC ≤Grade 1 on Day 1 and/or ANC ≤Grade 2 on Day 8 or 15	Continue at current dose level.

Platelets  $\geq$ Grade 2,  
ANC  $\geq$ Grade 2 on Day 1,  
ANC  $\geq$ Grade 3 on Day 8 or 15,  
and/or  
 $\geq$ Grade 3 platelets or ANC with  
spontaneous bleeding at any  
time

Withhold AK-01 until platelets  $\leq$ Grade 1 and ANC  
 $\leq$ Grade 1 (Day 1) or  $\leq$ Grade 2 (Day 8 or 15). Consider  
granulocyte colony stimulating factor (G-CSF) for low  
ANC. Decrease AK-01 dosing frequency when dosing is  
resumed.

Each time the Grade 3 event recurs, withhold AK-01  
until counts recover. Consider G-CSF for low ANC. If  

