### **5.4. Specific Restrictions/Requirements**

All patients must be available at the study center for approximately 8 hours on Day 1 of Cycle 1 for administration of the first dose of AK-01, PK sampling, and safety assessments. Patients must also be available at the study center for approximately 8 hours after the first dose on Day 15 of Cycle 1 in order to perform PK sampling and safety assessments.

Tumor biopsy will involve observation for safety monitoring according to the institutional standard of care (typically 4-6 hours).

Periodic visits to the study center will also be necessary as described in the schedule of events (Appendix 1).

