### 9.9.5. Dose Proportionality

Dose proportionality will be evaluated for Cmax, AUC0-12, AUC0-24, and AUC0-∞ for study arms in Phase I. Dose proportionality will be evaluated after dosing on Day 1 and Day 15, separately. A power model (regression of log-transformed data) will be fit on Day 1 and Day 15, separately, to describe the relationship between PK parameters (Cmax, and AUCs) and dose. Dose proportionality will be concluded when the ratio of dose-normalized geometric mean values (Rdnm) lies entirely within (0.80, 1.25), that is 90% CIs of the slope  $\beta$  lies entirely within  $(1+\ln(0.8)/\ln(r), 1+\ln(1.25)/\ln(r))$ , where  $r$  is a ratio that describes the dose range and is defined as the ratio of (highest dose/lowest dose). For each model, the predicted geometric mean PK parameter values, Rdnm, maximum proportional dose range ( $\rho_1$ ) and threshold dose ratio to reject proportionality ( $\rho_2$ ) will be reported based on the estimates from the power model [6].

Results for the dose proportionality analysis of all parameters will be shown also graphically.

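### AUC0-24 is built from AUC0-12 with no limit by day or regimen: it is too low on Day 1, and if AUC0-12 is doubled it is too high in patients already reduced to once daily

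*SAP*

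**What the plan says.** Protocol 8.1.3 names AUC0-24 among the four primary PK parameters. SAP 9.9.4 says that "PK parameters for Day 1 and 15 will be calculated individually by standard non-compartmental methods of analysis", and it defines AUC0-24 as "Area under the plasma concentration versus time curve from time 0 to 24 hours post-dose, based on AUC0-12 data". No multiplier is given. CL/F is Dose divided by AUC0-24, and Vz/F is the same quantity divided by kel. Both are marked as Day 15 only; AUC0-24 carries no such mark. Dose is not defined.

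SAP 9.9.5 lists AUC0-24 among the dose-proportionality parameters and states: "Dose proportionality will be evaluated after dosing on Day 1 and Day 15, separately".

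Dosing is BID on every day of the cycle (Protocol 5.2.2). The full profile on Days 1 and 15 consists of "PK concentrations at 0 hours (pre-dose) and 1, 2, 4, 6, and 8-12 hours post-dose" (SAP 9.9.2). The only other Cycle 1 samples are pre-dose troughs on Days 2 and 8, so hours 12 to 24 are never profiled.

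Protocol Table 1 allows a change of frequency during treatment, for example "Reduce dosing frequency without interruption" for Grade 2 QTcF prolongation. The text below the table limits reduction to 25 mg BID going to 25 mg QD. SAP 9.9.4 summarises Phase II parameters by tumor type, with no split by regimen, and the PK Analysis Set has no rule for QD patients.

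**The concern.** A 24-hour area taken from a 12-hour profile is sound only if the second 12 hours repeat the first. That is true at BID steady state. It is not true on Day 1, when the patient starts from zero, nor in a patient who takes one dose a day. The SAP makes no distinction, so the same rule would be programmed for all three situations.

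At stake are the Day 1 summaries of a parameter that the protocol calls primary and, in Phase II, the Day 15 AUC0-24, CL/F and Vz/F of any patient already on QD, pooled with BID patients of the same tumor type. PK is a secondary objective in Phase II and exploratory in Phase I.

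**Working it through.** The plan states no AUC, half-life or clearance, so there is no figure to reproduce. The direction follows from algebra. The size needs assumptions.

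**Inputs from the documents:** BID dosing from Day 1 (Protocol 5.2.2); profile to 8-12 h on Days 1 and 15 (SAP 9.9.2); AUC0-24 from AUC0-12 on both days (SAP 9.9.4); QD possible before Day 15 (Protocol Table 1).

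**Assumed, not in the documents:** AUC0-24 = 2 x AUC0-12; one compartment with first-order absorption, ka = 1/h; half-life 2 to 24 h.

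**Notation.** F(t) is the share of a single dose's AUC0-∞ reached by time t. With k = ln 2 / half-life,

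F(t) = 1 − [ka·e^(−kt) − k·e^(−ka·t)] / (ka − k).

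**Day 1, BID.** By superposition, true AUC0-24 = F(24) + F(12) = 2F(12) + [F(24) − F(12)]. Doubling drops the bracket, the 12-24 h tail of dose 1, so it is always low:

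doubled / true = 2F(12) / [F(12) + F(24)].

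Extending the morning curve to 24 h gives F(24), which omits the evening dose and is also low.

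Example at 8 h: k = 0.0866, F(12) = 0.613, F(24) = 0.863, ratio = 1.226 / 1.476 = 0.83.

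**Day 15, BID steady state.** AUC0-12 = AUC12-24, so doubling is exact. Over a grid of half-life 2-48 h and ka 0.15-2/h the Day 15 ratio is 0.999-1.000.

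**Day 15, QD steady state.** The share S of the 24 h area that falls in the first 12 h is

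S = [ka/(1 + e^(−12k)) − k/(1 + e^(−12ka))] / (ka − k).

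Doubled / true = 2S. True CL/F is 25 mg over the true AUC0-24. Relative to that, CL/F from the doubled area is 1/(2S) if Dose is the 25 mg taken, and 1/S if it is the assigned 50 mg.

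| Half-life (h) | F(12) | F(24) | Day 1 doubled/true | S | QD doubled/true | QD CL/F, Dose 25 mg | QD CL/F, Dose 50 mg |
|---|---|---|---|---|---|---|---|
| 2 | 0.976 | 1.000 | 0.99 | 0.976 | 1.95 | 0.51 | 1.02 |
| 4 | 0.849 | 0.981 | 0.93 | 0.866 | 1.73 | 0.58 | 1.16 |
| 8 | 0.613 | 0.863 | 0.83 | 0.714 | 1.43 | 0.70 | 1.40 |
| 12 | 0.469 | 0.735 | 0.78 | 0.646 | 1.29 | 0.77 | 1.55 |
| 24 | 0.272 | 0.485 | 0.72 | 0.573 | 1.15 | 0.87 | 1.74 |

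Over the wider grid, with the switch to QD placed at Day 8, the Day 1 ratio runs from 0.57 to 0.99 and the QD ratio from 1.02 to 1.96. Neither changes direction.

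**Dose in BID patients.** 50 mg over 2 x AUC0-12 equals 25 mg over AUC0-12, and both are right. Using 25 mg over the doubled area halves CL/F. The SAP does not say which is meant.

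**Dose proportionality.** log(2 x AUC0-12) = log 2 + log AUC0-12. Only the intercept of the power model moves; the slope and its confidence interval are those of AUC0-12.

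**End of the profile.** Protocol 5.4 asks patients to be "available at the study center for approximately 8 hours after the first dose on Day 15 of Cycle 1", so the last draw may come near 8 h. AUC0-12 then needs a 12 h value. SAP 9.9.4 requires three points after Cmax for kel; with tmax at 4 h only the 6 h and 8-12 h samples remain.

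**The case against.** The formula is inferred. SAP 9.9.4 does not print doubling, and if the morning profile were extrapolated with kel instead, the QD overstatement would not follow. That stands, so the QD result is conditional on doubling. The Day 1 result is not, because both simple routes fall short. Adding an extrapolated tail to the doubled area would repair Day 1 in principle, but the SAP describes no such step and kel will not always be estimable.

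Little depends on Day 1 AUC0-24. CL/F and Vz/F use Day 15, the hematology correlations use Day 15 AUC0-12, Cmax and Cavg, and the Phase II dose is already chosen. This stands and limits the consequence.

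The QD group is narrow. Scheduled Cycle 1 ECGs on treatment fall only on Days 1 and 15, so the QTcF route needs a Day 1 post-dose reading or an unscheduled ECG. The hematologic route needs withholding, recovery and resumption before Day 15. The sponsor may judge such data not interpretable, and the Phase II mean plots are already split by dose. All true, but no written rule covers the parameter tables.

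Three stronger readings are tempting and not supported:

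- **CL/F is too low in QD patients.** This holds only if Dose is the 25 mg taken. With the assigned 50 mg it is too high.
- **Accumulation would be overstated.** The planned ratio uses AUC0-12, and no Day 15 to Day 1 comparison of AUC0-24 is planned. If both were doubled, their ratio would equal the AUC0-12 ratio.
- **The dose-proportionality result for AUC0-24 is biased.** Under doubling it merely repeats the AUC0-12 result.

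**Conclusion.** The definition is valid for one situation, Day 15 in patients on uninterrupted BID dosing, and the SAP applies it without that limit. Day 1 AUC0-24 is too low by either simple route: under doubling by about 7% to 28% for half-lives of 4 to 24 h, and by only about 1% at 2 h. If AUC0-12 is doubled, AUC0-24 is about 15% to 73% too high over the 4 to 24 h range in each patient already on QD by Cycle 1 Day 15. These are per-patient errors, not the bias of a cohort summary; the number of such patients is unknown. CL/F and Vz/F in those patients are wrong in a direction set by the undefined Dose.

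The sizes rest on a one-compartment model with ka 1/h and assumed half-lives. The Day 1 direction needs neither that model nor the inferred multiplier; the QD direction needs doubling. The ORR analysis is untouched. The change is worth making because the parameter is named as primary for PK and the correction is simple.

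**What to change.** In SAP 9.9.4:

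- State AUC0-24 = 2 x AUC0-12. Report it on Day 15 only, and only for patients on uninterrupted BID dosing. Do not report Day 1 AUC0-24.
- Define Dose. For BID patients compute CL/F as the single dose over Day 15 AUC0-12, and Vz/F as that value divided by kel.
- Do not apply the doubled AUC0-24, or CL/F and Vz/F based on it, to QD or interrupted patients. The linearity index uses Day 15 AUC0-24 and takes the same limit.
- Summarise Phase II Day 15 parameters by actual regimen within tumor type.
- Where an uninterrupted BID patient's last Day 15 draw is before 12 h, the Day 15 pre-dose concentration can serve as the 12 h value.
- Keep the accumulation ratio on AUC0-12. Moving it to AUC0-8 because of early last draws would shift it by about 1% to 4% in the same model and is not needed.

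In SAP 9.9.5, drop AUC0-24. In SAP section 2, record the change, since Protocol 8.1.3 lists the parameter as primary.

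The cost is SAP wording and PK programming, with no new samples. The downside is fewer reported AUC0-24 values, and none for QD patients unless a separate method for hours 12 to 24 is specified.

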### 5.2.2. Dose and Regimen

AK-01 will be administered twice daily, every day of a 21-day cycle. Patients will be dosed continuously: there will be no dosing holiday between cycles.

In Phase I, the dose of AK-01 will be between 25-75 mg BID per day (see [Table 3](#)). Patients in the first cohort of Phase I will receive 25 mg BID AK-01. Following a review of safety and other relevant data from this cohort, the SAC will decide on the dose for the subsequent cohort based on [Table 3](#). Following DLT or completion of Cycle 1, dosing for a given patient will be based on individual safety and tolerability.

For Phase II, the sponsor and SAC has established the dose of AK-01 as 25mg BID.

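### SAP 9.9.4 and 9.9.5 derive AUC0-∞ on Day 15 and test it for dose proportionality, although after two weeks of twice-daily dosing it is not a single-dose exposure (minor)

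*SAP*

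**What the plan says.** SAP 9.9.4 states that "PK parameters for Day 1 and 15 will be calculated individually by standard non-compartmental methods of analysis". AUC0-∞ is in that list, defined as "Area under the plasma concentration versus time curve from time 0 to infinity using the linear trapezoidal rule, calculated as" AUC0-t + Clast/kel, with no restriction by day.

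The same list does use day restrictions elsewhere. CL/F and Vz/F are marked for Day 15 only, and the linearity index takes its AUC0-∞ from Day 1. The only stated reason to withhold AUC0-∞ is the closing rule of 9.9.4, under which it and some other parameters "will not be reported for cases that do not exhibit a terminal log-linear phase of the concentration-time curve". Parameters are summarised by dose level and day in Phase I and by tumor type in Phase II.

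SAP 9.9.5 states: "Dose proportionality will be evaluated for Cmax, AUC0-12, AUC0-24, and AUC0-∞ for study arms in Phase I". It adds: "Dose proportionality will be evaluated after dosing on Day 1 and Day 15, separately".

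On dosing, Protocol 5.2.2 says: "AK-01 will be administered twice daily, every day of a 21-day cycle". There is no break between cycles, and Protocol 5.2.1 puts the doses about 12 hours apart. SAP 9.9.2 schedules samples on Days 1 and 15 before the dose and at 1, 2, 4, 6 and 8-12 hours after it.

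**The concern.** AUC0-∞ measures exposure to one dose only when no drug is present at time zero. That holds on Day 1. On Day 15 the pre-dose concentration and the extrapolated tail both contain drug from earlier doses. The tail also describes a period that never occurs without further drug, because the next dose is due at about 12 hours. A programmer following the SAP as written would produce this quantity, tabulate it under the same name as the Day 1 value, and fit a power model to it.

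Two outputs are at stake. One is the Day 15 AUC0-∞ row in the PK summaries of both phases. The other is the Day 15 AUC0-∞ result in the Phase I proportionality analysis.

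**Working it through.** The plan states no half-life, accumulation ratio or AUC value, so there is no figure of its own to reproduce.

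**Inputs.** Dosing interval 12 h (Protocol 5.2.1). Scheduled doses before the Day 15 morning dose: 14 days × 2 = 28. Phase I dose range 25-75 mg BID (Protocol 5.2.2), so r = 75/25 = 3. Half-life is assumed and shown as a range.

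**Step 1: size of the inflation.** Take a mono-exponential curve with k = ln 2 / half-life. The single-dose AUC0-∞ is C0/k. At steady state the concentration just after a dose is C0/(1 − e^(−12k)), so extrapolating from there to infinity gives C0/[k(1 − e^(−12k))]. The ratio of Day 15 to single-dose AUC0-∞ is 1/(1 − e^(−12k)).

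| Assumed half-life | e^(−12k) | Ratio |
|---|---|---|
| 2 h | 0.016 | 1.02 |
| 4 h | 0.125 | 1.14 |
| 6 h | 0.250 | 1.33 |
| 12 h | 0.500 | 2.00 |
| 24 h | 0.707 | 3.41 |

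Two checks agree. Superposing 29 doses in a one-compartment oral model (absorption rate assumed 1.5 per hour) gives 1.02, 1.16, 1.36, 2.04 and 3.46. Applying the SAP's own rule (linear trapezoid plus Clast/kel) at the planned sampling times gives about 1.02, 1.17, 1.37, 2.04 and 3.4. Most of the carry-over is recent: 95% comes from the last 5 doses at a 12 h half-life and from the last 9 at 24 h.

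**Step 2: what the planned AUC0-12 gives.** In the same oral model the Day 15 area over one dosing interval, divided by single-dose AUC0-∞, is 1.00 for half-lives of 2 to 24 h and 0.99 at 48 h. The single-dose exposure is therefore already available on Day 15 as AUC0-12.

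**Step 3: the proportionality slope.** SAP 9.9.5 sets slope limits of 1 + ln(0.8)/ln(3) = 0.797 and 1 + ln(1.25)/ln(3) = 1.203.

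- *kel the same at every dose.* The ratio from Step 1 is constant across doses and cancels. The slope is 1.000.
- *Clearance and kel fall together by 15% from 25 to 75 mg, half-life 12 h at 25 mg.* For AUC over the dosing interval, the 75:25 ratio is 3/0.85 = 3.529 and the slope is ln(3.529)/ln(3) = 1.148. For Day 15 AUC0-∞, the inflation is 1/(1 − 0.5) = 2.000 at 25 mg and 1/(1 − 0.5^0.85) = 2.246 at 75 mg. The ratio is then 3.529 × 2.246/2.000 = 3.964, and the slope is ln(3.964)/ln(3) = 1.254.
- *Same 15% fall, other half-lives at 25 mg.* The AUC0-∞ slope is 1.197 at 4 h (still inside the limits), 1.221 at 6 h and 1.273 at 24 h (both outside).
- *A 10% fall.* The slope is 1.096 for AUC over the interval, against 1.126 (4 h) to 1.177 (24 h) for Day 15 AUC0-∞. All are inside the limits.

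**The case against.** The strongest reply is that little depends on this value. Protocol 8.1.3 names AUC0-12, AUC0-24, Cmax and tmax as the primary PK parameters and does not list AUC0-∞. PK is exploratory in Phase I, and the Phase II dose has already been chosen (Protocol 1.3). The table shells are a separate document, so it cannot be checked whether a Day 15 AUC0-∞ row will be displayed. All of this stands, and it limits the severity. It does not remove the point, because 9.9.4 and 9.9.5 read literally require the calculation and the test.

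A reader might infer more than the documents support, in four ways:

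- *That the Day 15 test would call a linear drug non-linear.* It would not: the factor cancels when kel does not depend on dose. Where kel does change with dose, Day 15 AUC0-∞ exaggerates a real departure that AUC over the dosing interval also shows.
- *That the plan's clearance or accumulation results are corrupted.* SAP 9.9.4 computes CL/F and Vz/F from AUC0-24, the linearity index from Day 1 AUC0-∞, and the accumulation ratios from AUC0-12 and Cmax. None uses Day 15 AUC0-∞.
- *That a Phase II secondary objective is put at risk through the proportionality test.* That test covers Phase I only. In Phase II the effect is confined to a descriptive row.
- *That patients reduced to once daily add scatter which dropping AUC0-∞ would cure.* At a 12 h half-life the once-daily to twice-daily ratio is 1.33/2.00 = 0.67 for AUC0-∞, and (0.5/0.75)/1.0 = 0.67 for AUC0-12, so the substitution changes nothing. Protocol 3.3.2 also ties the 25 mg once-daily step to the Phase II dose, and nothing shows Phase I patients on once-daily dosing by Day 15.

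**Conclusion.** The point holds as a minor one. As written, the SAP derives on Day 15 an AUC0-∞ that is not a single-dose exposure and cannot be compared with the Day 1 value of the same name. Its excess is about the accumulation factor: negligible at a 2 h half-life, 2-fold at 12 h and 3.4-fold at 24 h. The documents do not allow a choice within that range. The size rests on linear kinetics, near steady state by Day 15, and no missed doses.

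For proportionality the effect is conditional. It is nil if kel does not depend on dose. If clearance and kel fall with dose, it can carry the slope from inside the limits to outside. SAP 9.9.5 requires the whole 90% confidence interval to lie within the limits, so a slope of 1.254 cannot pass. A slope of 1.148 passes only if the interval extends less than 1.203 − 1.148 = 0.055 above it. Whether the formal conclusion would differ therefore also depends on precision, and only 12 patients had been dosed when Protocol 1.3 was written.

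**What to change.** In SAP 9.9.4, mark AUC0-∞ as Day 1 only, in the same style as the existing day limits on CL/F and Vz/F. In SAP 9.9.5, keep AUC0-∞ in the Day 1 analysis and remove it from the Day 15 set, leaving Cmax, AUC0-12 and AUC0-24, which are already planned. Align the table shells if they show a Day 15 AUC0-∞ row.

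The cost is two lines of SAP wording. No sampling or data collection changes, and no interpretable result is lost, because Day 15 AUC0-12 already gives the single-dose exposure under linear kinetics at steady state.

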the event recurs at 25 mg QD, the patient will be  
withdrawn.

**The sponsor must be notified of dose reductions. Given the P2D of 25mg BID, the only dose reduction allowed will be a reduction in dosing frequency from 25mg BID to 25mg QD.**

Following dose reduction and recovery, re-escalation of a patient's dose will be at the discretion of the sponsor in discussion with the investigator. Re-escalation must not exceed the dose at which toxicity was experienced.

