### 5.2.1. Investigational Medicinal Product Administration

Doses of AK-01 taken at the study center will be administered by trained study personnel and will be recorded. Any dose reductions or dose interruptions will be recorded with the associated reasons. Patients will be given instructions for home dosing. Confirmation of home administration will be based on measurements of treatment compliance (see [Section 8.1.5](#)).

AK-01 should be taken orally according to the assigned dosing schedule and the investigator's instructions. Patients will take AK-01 twice a day approximately 12 hours apart. Patients will be encouraged to fast for 1 hour prior and 1 hour following each dose.

Doses of AK-01 should be taken at approximately the same time each day during the dosing period. If a dose of AK-01 is missed, it should be reported as such and should not be combined with a dose on another day. If a dose of AK-01 is vomited, it should be reported as such and should not be repeated.

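### The SAP's linearity index divides a two-dose exposure by a one-dose exposure, so linear PK on twice-daily dosing returns about 2, and the SAP gives no reference value

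*SAP*

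**What the plan says.** SAP section 9.9.4 lists the PK parameters for Day 1 and Day 15 of Cycle 1. The linearity index is defined as "Linearity index, calculated as: $AUC0-24 [Day 15] / AUC0-∞ [Day 1"]. Its numerator, AUC0-24, is defined as "Area under the plasma concentration versus time curve from time 0 to 24 hours post-dose, based on AUC0-12 data". Its denominator is the Day 1 AUC to the last quantifiable concentration plus an extrapolated tail.

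The accumulation ratio in the same list is "Accumulation ratio (based on AUC), calculated as $AUC0-12$ after last dose on Day 15 / $AUC0-12$ after a single dose [Day 1"]. It sets one 12-hour interval against another, and it describes Day 1 as a single dose.

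On dosing, protocol section 5.2.1 says "Patients will take AK-01 twice a day approximately 12 hours apart", and section 5.2.2 says "AK-01 will be administered twice daily, every day of a 21-day cycle". On sampling, SAP section 9.9.2 has "For Day 1 and 15 (Cycle 1): PK concentrations at 0 hours (pre-dose) and 1, 2, 4, 6, and 8-12 hours post-dose". Protocol Appendix 1 (PK sampling footnote) ties these times to the first dose of each of those days.

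The SAP gives LI no expected value, threshold or rule for interpretation. It does not report LI where the concentration-time curve shows no terminal log-linear phase.

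**The concern.** An index of linearity needs a known value that means linear. The usual comparison rests on one identity: if PK is linear and does not change with time, the steady-state AUC over one dosing interval equals the single-dose AUC0-∞. That calls for one dose on each side of the ratio. Here the numerator covers a whole day on twice-daily dosing, which is two doses, and nothing corrects for that.

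A reader who takes 1 as the mark of linearity would read a linear drug's value near 2 as exposure twice that predicted from the first dose. The same reader would take a real doubling of apparent clearance by Day 15 as linear behaviour. What is at stake is how one PK parameter is described in the study report.

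**Working it through.** The SAP states no figure for LI, so there is nothing to reproduce. The check derives what the formula returns when PK is exactly linear.

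**Inputs from the documents.** Dosing interval 12 h (protocol 5.2.1, 5.2.2). Numerator AUC0-24 on Day 15; denominator AUC0-∞ on Day 1; elimination rate constant (kel) from at least 3 points, not including Cmax (SAP 9.9.4). Samples at 0, 1, 2, 4, 6 and 8-12 h (SAP 9.9.2).

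**Assumed inputs.** The documents give neither half-life nor absorption rate (ka). I used half-lives of 3, 6, 12, 24 and 48 h and ka of 0.5, 1 and 2 per hour, which makes 15 scenarios, in a one-compartment oral model with superposition. There are 28 doses before the Day 15 morning dose.

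**Algebra.**
- Day 1, one dose: AUC0-∞ = F × Dose / CL.
- Day 15, steady state, one interval: AUC0-12 = F × Dose / CL.
- Day 15, two intervals: AUC0-24 = 2 × F × Dose / CL.
- LI as written = 2 × (CL/F on Day 1) / (CL/F on Day 15).
- CL/F unchanged: LI = 2. CL/F doubled: LI = 2 × 1/2 = 1.

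Half-life cancels, so the factor of 2 does not depend on AK-01's kinetics once steady state is reached.

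**Numerical check, linear PK, exact AUCs (same at every ka).**

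| Half-life | As written | AUC0-12 in numerator |
|---|---|---|
| 3, 6, 12, 24 h | 2.00 | 1.00 |
| 48 h | 1.99 | 0.99 |

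At 48 h, Day 15 is just short of steady state.

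**Clearance doubled from Day 8 (assumed, ka 1 per hour).** As written 1.00 to 1.01; with AUC0-12, 0.50.

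**With the SAP's sampling and NCA rules.** I used the linear trapezoid, the last sample at 8 or 12 h, and AUC0-24 taken as 2 × AUC0-12. Where the last sample is at 8 h, the 12-h value is extrapolated log-linearly. Three points after Cmax are available in 8 of the 15 scenarios. In those, the index as written is 1.85 to 2.02, and the matched index is half that, 0.93 to 1.01. In the other 7, kel cannot be estimated and LI would be missing.

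**Does changing the numerator suffice?** Not for every patient. Protocol 3.3.2 allows drug to be withheld for up to 21 days. Its Table 1 lets a patient resume at the same dose level after a first Grade 3 non-hematologic event. Such a patient is on twice-daily dosing on Day 15 but may not be at steady state. With an assumed 7-day hold, ka 1 per hour and exactly linear PK, the matched index at half-lives of 3, 6, 12 and 24 h is:
- Day 15 morning dose is the first dose back: 0.92, 0.72, 0.47, 0.28.
- One dose taken before it after restart: 0.99, 0.93, 0.73, 0.49.

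Patients moved to once-daily dosing are also on a different scale (protocol 3.3.2: "the only dose reduction allowed will be a reduction in dosing frequency from 25mg BID to 25mg QD"). With the change assumed on Day 8, the matched index would read 0.92, 0.77, 0.65 and 0.58 at the same half-lives. The parameter summary is specified "for Phase I and by tumor type for Phase II, separately", so for Phase II nothing in that sentence separates these patients.

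**The case against.** The strongest defence is that the SAP never says LI should equal 1. No stated figure is wrong. The formula is in print, the factor is known and constant, and the output shells, held in a separate document, might carry an explanatory footnote. All of that is fair, and it limits the harm to a reader who does not check the formula. It does not remove the mismatch: an index named for linearity reads 2 for a linear drug, and the text that defines it does not say so.

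A second defence is that AUC0-24 might be built in some way other than doubling. The SAP says only that it is based on AUC0-12, so doubling is an assumption, though a natural one. A true 24-hour AUC on twice-daily dosing also gives 2 at steady state, so the conclusion does not turn on it.

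Three stronger readings are tempting and should be resisted.
- A reader might infer that a value of 1 can arise only if clearance has doubled. Halved bioavailability gives the same value, and a Day 15 profile short of steady state after a hold also lowers the index.
- A reader might infer that the SAP contradicts its own benchmark. It has none; the fault is a mismatched definition with no reference value.
- A reader might infer that the trial's PK conclusions are compromised. Accumulation is measured by interval-matched ratios, and dose proportionality by a separate power model (SAP 9.9.5) that does not use LI.

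**Conclusion.** The formula is wrong as written, and the error is minor. For patients at steady state on twice-daily dosing it is a constant factor of 2, so coefficients of variation and the ranking of patients do not change. LI is descriptive, has no threshold or decision role, and is not named among the PK parameters in the protocol synopsis or section 8.1.3. It is reported only where a terminal log-linear phase exists, which may leave it missing for many patients. ORR, DLT, accumulation-ratio and dose-proportionality results are unaffected.

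The factor of 2 rests on twice-daily dosing, steady state on Day 15 and linear, time-invariant PK. It does not rest on the assumed half-lives. The figures for sampled profiles, dose holds and once-daily patients do rest on assumed half-life, absorption rate and timing. The number of patients with a hold or a frequency reduction before Day 15 is unknown and probably small.

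**What to change.** Replace the LI entry in SAP section 9.9.4 with:

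> LI = AUC0-12 [Day 15] / AUC0-∞ [Day 1], summarized for patients on uninterrupted BID dosing at an unchanged dose for long enough before Day 15 to be at steady state. A value of 1 is expected under linear, time-invariant PK. Patients on QD dosing, or with a recent dose hold or dose change before Day 15, are listed separately and not included in the LI summary.

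The sponsor should set how long counts as long enough from the observed half-life, since the documents do not give one.

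The cost is one formula, one sentence on the expected value and one listing rule, in the SAP and in the PK laboratory's program, with perhaps a small change to the output shells. No new samples are needed. Any LI values already calculated must be recomputed (simply halved if AUC0-24 was taken as 2 × AUC0-12), and a few patients drop out of the LI summary.
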